7.7.3 Graphical Presentation of PD Data

Boxplots of change from time-matched baseline in 24-hour, daytime, and 4-hour averages of ambulatory systolic BP, mean arterial pressure, diastolic BP, and pulse will be presented by treatment group. Least squares mean plots of change from time-matched baseline in the above parameters as well as for the 30-minute averages of ABPM assessments over time along with the corresponding 95% confidence intervals will be plotted by treatment group.

Least squares mean plots of change from trough baseline in trough supine cuff blood pressure and pulse assessments over time, along with the corresponding 95% confidence intervals will be presented by treatment group. Bar graphs will be presented by study day and treatment group for the proportion of patients meeting target supine blood pressure criteria.

Boxplots of change from study baseline will be presented by treatment group for endothelial function, HOMA-IR, metabolic, platelet function, and exploratory vascular physiology parameters. Bar graphs will be presented by treatment group for the proportion of patients with decreased platelet reactivity.

7.8 PHARMACOKINETIC (PK) ANALYSIS

7.8.1 PK Parameters

The PK parameters listed in [Table 3](#) will be calculated for each patient, whenever possible, if systemic levels of IW-1973 are quantifiable. PK parameter calculations will be performed using noncompartmental methods with Phoenix® WinNonlin® Version 6.4, or higher, (Certara L.P., Princeton, New Jersey, United States).

Plasma concentrations that are below the lower level of quantification (LLQ) or missing will be treated as described in [Section 9.7](#) for the calculation of PK parameters. Actual sampling times relative to IW-1973 dosing times will be used in calculations of the PK parameters. Area under the concentration-time curve will be calculated by linear up/log down trapezoidal summation.

Table 3. PK Parameters

Parameter	Description
	To be calculated on Day 1 relative to the morning dose, unless otherwise noted
AUC _{last}	Area under the plasma concentration time curve from time zero to T _{last} , the time at which the last measurable plasma concentration (C _{last}) is observed.
AUC _{tau}	Area under the plasma concentration-time curve during a dosing interval (tau: 24 hours for QD regimen, 12 hours for BID). Actual elapsed time at tau will be used for the calculation. If the IW-1973 sample at the end of the dosing interval is missing, AUC _{tau} will not be determined. If the IW-1973 sample at the end of the dosing interval is BLQ, AUC _{all} will be used to describe AUC _{tau} . For the BID regimen, this parameter will be calculated for the morning and for the evening dose, and for the 24-hour sampling period on Day 1 (AUC ₂₄).
AUC _{tau} /D	Dose-normalized AUC _{tau} . For the BID regimen, this parameter will be calculated for the morning dose and overall for the 24-hour sampling period (AUC ₂₄).
T _{max}	Time of maximum observed plasma concentration, obtained directly from the concentration-time profile. For the BID regimen, this parameter will be calculated for the morning and for the evening dose.
C _{max}	Maximum observed plasma concentration, occurring at T _{max} . For the BID regimen, this parameter will be obtained from the observed concentration-time data for the morning and for the evening dose as well as overall (C _{max,24}) for the 24-hour sampling period.
C _{max} /D	Dose-normalized C _{max}
C _{trough}	Trough plasma concentration observed at the end of a dosing interval (collected before the next administration) and will be correspond to the following sample collection times: 
 • 24-hour trough following the QD dose on Day 1: Day 2 predose • 12-hour troughs following the BID doses on Day 1: Day 1 PM predose and Day 2 AM predose
	To be calculated on Day 7 relative to the morning dose, unless otherwise noted
AUC _{last}	Area under the plasma concentration time curve from time zero to T _{last} , the time at which the last measurable plasma concentration (C _{last}) is observed
AUC _{tau}	Area under the plasma concentration-time curve during a dosing interval (tau: 24 hours for QD regimen, 12 hours for BID). Actual elapsed time at tau will be used for the calculation. If the IW-1973 sample is missing either at the beginning or at the end of the dosing interval, AUC _{tau} will not be determined. If the IW-1973 sample at the end of the dosing interval is BLQ, AUC _{all} will be used to describe AUC _{tau} .
AUC _{tau} /D	Dose-normalized AUC _{tau}
RAUC _{tau}	Accumulation ratio of AUC _{tau} comparing Day 7 with Day 1
T _{max}	Time of maximum observed plasma concentration
C _{max}	Maximum observed plasma concentration, occurring at T _{max}
RC _{max}	Accumulation ratio of C _{max} comparing Day 7 with Day 1
C _{max} /D	Dose-normalized C _{max}

Table 3. PK Parameters

Parameter	Description
C_{trough}	Trough plasma concentration observed at the end of a dosing interval (collected before the next administration) and will be correspond to the following sample collection times: 
 • 24-hour trough following the QD dose on Day 6: Day 7 predose • 24-hour trough following the QD dose on Day 7: Day 8 predose • 12-hour trough following the evening BID doses on Day 6: Day 7 predose • 12-hour troughs following the BID doses on Day 7: Day 7 PM predose and Day 8 predose
RC_{trough}	Accumulation ratio for C_{trough} comparing the trough following the IW-1973 dose on Day 7 with the trough following the IW-1973 dose on Day 1, calculated as: Day 8 morning predose concentration / Day 2 morning predose concentration. Note: for the BID regimen, this comparison is made relative to the trough following the evening doses on Days 7 and 1.
To be calculated on Day 8	
AUC_{last}	Area under the plasma concentration time curve from time zero to T_{last} , the time at which the last measurable plasma concentration (C_{last}) is observed
C_{max}	Maximum observed plasma concentration, occurring at T_{max}
SC_{max}	Ratio of C_{max} obtained after switching to the 40 mg QD regimen on Day 8 divided by C_{max} following the morning 20 mg BID dose on Day 7 (BID/QD regimen)
C_{max}/D	Dose-normalized C_{max}
T_{max}	Time of maximum observed plasma concentration
To be calculated on Day 14	
AUC_{last}	Area under the plasma concentration time curve from time zero to T_{last} , the time at which the last measurable plasma concentration (C_{last}) is observed
AUC_{tau}	Area under the plasma concentration-time curve during a dosing interval (tau: 24 hours). Should either the predose or the 24-hour postdose sample be missing, the concentration of the other sample (eg, predose for missing 24 hour) will be substituted for calculation of AUC_{tau} .
AUC_{tau}/D	Dose-normalized AUC_{tau}
$RAUC_{tau}$	Accumulation ratio of AUC_{tau} comparing Day 14 with Day 1, calculated as 
 • QD/QD regimen: Day 14 AUC_{tau} / Day 1 AUC_{tau} • QD/BID regimen: Day 14 AUC_{tau} / Day 1 AUC_{24}
C_{max}	Maximum observed plasma concentration, occurring at T_{max}
RC_{max}	Accumulation ratio of C_{max} comparing Day 14 with Day 1 calculated for the QD/QD regimen only
C_{max}/D	Dose-normalized C_{max}

Table 3. PK Parameters

Parameter	Description
C_{trough}	Trough plasma concentration observed at the end of a dosing interval (collected before the next administration) and will be correspond to the following sample collection times: 
 • 24-hour trough following the QD dose on Day 13: Day 14 predose • 24-hour trough following the QD dose on Day 14: Day 14 24-hours postdose
RC_{trough}	Accumulation ratio for C_{trough} comparing the trough following the IW-1973 dose on Day 14 with the trough following the IW-1972 dose on Day 1, calculated as: Day 14 24-hour postdose concentration / Day 2 morning predose concentration. Note: for the BID regimen, this comparison is made relative to the trough following the evening dose on Day 1 (ie, following the total daily dose of 40 mg)
CL/F	Apparent total body clearance after oral administration, calculate as the administered dose divided by AUC_{tau} . No dose adjustment is required in this calculation.
$t_{1/2}$	Apparent terminal phase half-life, determined by linear regression of the terminal points of the log-linear concentration-time curve. A minimum of 3 data points will be used for determination. This parameter will be calculated but not included in any summaries if goodness of fit statistic for calculation of the regression coefficient (Rsq) for the elimination rate (λ_z) is less than 0.800. Interval of the log-linear regression, number of data points, Rsq, and λ_z will be reported for diagnostic purposes.
$t_{1/2, eff}$	Effective half-life, calculated as $\ln(2) * (-24) / [\ln(1 - \{1/RAUC_{tau}\})]$
T_{max}	Time of maximum observed plasma concentration
V_z/F	Apparent volume of distribution during the terminal phase after oral administration calculated as $CL/F / \lambda_z$

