3.2 TREATMENTS ADMINISTERED

Patients will be randomized in a 5:5:3 ratio to 1 of 2 IW-1973 treatment regimens or placebo (all regimens will be masked) as outlined in [Table 1](#).

Table 1. Treatment Arm Dosing Regimens

Treatment Arm	Dose time	Days 1 to 7	Days 8 to 14
PBO/PBO	AM	Placebo (8 x placebo tablet)	Placebo (8 x placebo tablet)
	PM	Placebo (8 x placebo tablet)	Placebo (8 x placebo tablet)
BID/QD	AM	20 mg IW-1973 (4 x IW-1973 Tablet*) (4 x placebo tablet)	40 mg IW-1973 (8 x IW-1973 Tablet*)
	PM	20 mg IW-1973 (4 x IW-1973 Tablet*) (4 x placebo tablet)	Placebo (8 x placebo tablet)
QD/QD	AM	40 mg IW-1973 (8 x IW-1973 Tablet*)	40 mg IW-1973 (8 x IW-1973 Tablet*)
	PM	Placebo (8 x placebo tablet)	Placebo (8 x placebo tablet)

PBO = Placebo, BID = twice daily, QD = once daily

* All IW-1973 tablets are 5 mg oral tablets

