7.8.2 PK Analysis

Plasma concentration of IW-1973 will be summarized using the PK Population for each assessment timepoint by active treatment groups. Concentrations that are below the limit of quantitation (BLQ) concentrations will be treated as zero for the computation of descriptive statistics. A by-subject listing of all concentration-time data for each treatment and scheduled sample collection time will be presented. A listing of PK blood sample collection times, and elapsed time relative to dose will be provided.

PK parameters will be summarized by treatment group using the PK Population. A by-subject listing of all PK parameters for each treatment and study day will be presented.

Changes to protocol procedures or events which may impact the quality of the PK data or alter the evaluation of the PK will be reviewed on a case-by case basis to determine if PK data

collected during the affected treatment period may be excluded from relevant PK summaries. Examples include, but may not be limited to, vomiting following oral dosing occurring within the time frame of 2 times the median time to maximum concentration (T_{max}), sample processing errors that lead to inaccurate bioanalytical results, missed doses and/or inaccurate dosing on or in relationship to the day of PK sampling. Deviations to procedures or events which do not impact the quality of the PK data such as a missed blood sample or deviations from blood collection times will not be considered for exclusion from PK summaries.

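### Day 14 trough accumulation ratio: 24-hour trough over 24-hour trough in QD/QD but over a 12-hour trough in BID/QD, so the two arms' values are not comparable (minor)

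*SAP*

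**What the plan says.** SAP section 7.8.1, Table 3, gives one Day 14 RC_trough formula for both regimens: "Day 14 24-hour postdose concentration / Day 2 morning predose concentration".

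- **Numerator.** The Day 14 C_trough row defines it as "24-hour trough following the QD dose on Day 14: Day 14 24-hours postdose". By then both active arms take 40 mg in the morning and placebo in the evening (SAP section 3.2, Table 1).
- **Denominator.** The Day 1 C_trough row labels the same clock-time sample differently by arm. For QD it is the "24-hour trough following the QD dose on Day 1: Day 2 predose". For BID the row reads "12-hour troughs following the BID doses on Day 1: Day 1 PM predose and Day 2 AM predose".
- **Note to the ratio.** The BID/QD denominator is explained as follows: "this comparison is made relative to the trough following the evening dose on Day 1 (ie, following the total daily dose of 40 mg". The note matches the arms on daily dose and says nothing about time since dose.
- **Neighbouring rows.** Day 14 RC_max is an accumulation ratio "comparing Day 14 with Day 1 calculated for the QD/QD regimen only". Day 7 RC_trough keeps the interval the same on both days within each arm; for BID, both samples follow an evening dose.
- **Reporting.** Section 7.8.2 states: "PK parameters will be summarized by treatment group using the PK Population". Section 6.1 makes a pooled IW-1973 overall column the default for PK parameters and sets out an exception only for Day 1. It also limits any inferential statistics to descriptive use.

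Neither document gives a half-life for IW-1973. SAP section 8 says only that a 24-hour profile is too short to characterize it adequately.

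**The concern.** An accumulation ratio isolates accumulation only if both samples are taken at the same time after the same dose. In QD/QD they are. In BID/QD half of the Day 1 dose was given 12 hours later than in QD/QD, so the Day 2 morning sample is higher by construction and the ratio lower.

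Comparing the PK profile of the two regimens is part of the objective (protocol section 2, SAP section 2). A table with the two ratios side by side invites the reading that starting with BID leads to less accumulation, when the difference comes from the definition. Any pooled column would average two different quantities under one name.

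**Working it through.** The plan states no value for this ratio, so there is no figure to reproduce. The check asks what the formula returns when both arms have identical linear pharmacokinetics.

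**Inputs from the documents**
- QD/QD: 40 mg every 24 h, 14 doses (SAP Table 1).
- BID/QD: 20 mg every 12 h, 14 doses, then 40 mg every 24 h, 7 doses (SAP Table 1).
- Day 2 AM predose sample: 24 h after the first dose.
- Final sample: the protocol's Discharge list (section 3.8.2.11) takes it 12 h postdose. The Day 14 evening dose is placebo in both arms, so the sample falls 24 h after the last active dose, at 336 h. The numerator is a true 24-hour trough.

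**Assumptions:** one compartment, linear kinetics, rapid absorption, half-life varied from 12 to 72 h.

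**Denominators.** Let x = 2^(−12/t½), the fraction left after 12 h.
- QD/QD: 40x²
- BID/QD: 20x² + 20x
- QD/QD over BID/QD: 2x/(1 + x), which equals 2/(1 + 2^(12/t½))

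**Numerators**
- QD/QD: 40(x² + x⁴ + … + x²⁸)
- BID/QD over QD/QD: [1 + x¹⁴(1 + 1/x)/2] / (1 + x¹⁴)
- At 24 h, x = 0.7071 and x¹⁴ = 0.0078, so this is (1 + 0.0078 × 1.2071)/1.0078 = 1.0016. The numerators are almost equal, so nearly all of the gap comes from the denominator.

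**Worked case, half-life 12 h.** x = 0.5. QD/QD: 1/(1 − 0.25) = 1.333. Denominator factor: 2 × 0.5/1.5 = 0.667. BID/QD: 1.333 × 0.667 = 0.889, which is 33% lower.

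| Assumed half-life | QD/QD | BID/QD | BID/QD lower by |
|---|---|---|---|
| 12 h | 1.333 | 0.889 | 33.3% |
| 18 h | 1.658 | 1.282 | 22.7% |
| 24 h | 2.000 | 1.659 | 17.0% |
| 36 h | 2.698 | 2.400 | 11.1% |
| 48 h | 3.388 | 3.119 | 7.9% |
| 72 h | 4.656 | 4.432 | 4.8% |

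**When BID/QD falls below 1.** Near steady state its ratio is 2x/[(1 + x)(1 − x²)]. Setting this to 1 gives 1 − x − x² − x³ = 0, so x = 0.544 and the half-life is about 13.7 h.

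**Sensitivity to the model**
- First-order absorption at 0.5 per h or faster changes the gap by 0.2 percentage points or less over the tabulated range.
- Slow absorption (0.25 per h) narrows it to 29.0% at 12 h, 13.7% at 24 h, 8.0% at 36 h and 5.1% at 48 h.
- With two-phase (biexponential) decline, the cases tried ran from about 5% to 47%.
- BID/QD was lower in every case.

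**Like-for-like quantities already in Table 3, same model**
- Day 7 RC_trough at a 24 h half-life: 1.984 in both arms. With slow absorption, BID/QD is about 2% higher.
- Day 14 24-hour C_trough, BID/QD over QD/QD: 1.000 to 1.010 for half-lives of 6 to 96 h.

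**The case against.** **The definition is deliberate and disclosed.** The authors restricted RC_max and annotated RC_trough, so this looks like a choice. Table 3 labels the two troughs openly as 12-hour and 24-hour. That stands, and the point should not be presented as an oversight. But the note says which sample is used; it does not tell the reader that the ratio cannot be compared between arms.

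**Little rests on this ratio.** No test or between-arm contrast of it is planned. Effective half-life is derived from RAUC_tau, and the scatterplots named in section 7.8.3 do not include RC_trough. A careful reader would also see similar Day 14 C_trough values in the two arms. This stands and is why the severity is minor. With no test planned, however, the descriptive values are themselves the result, so a bias built into the definition goes straight into the report.

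**Day 14 RAUC_tau already gives a matched measure for both arms.** Only partly so. It matches the 24-hour window and the daily dose, but on Day 1 the evening 20 mg contributes only 12 of those hours. In the same model at a 24 h half-life (absorption 1 per h) it reads 2.65 in BID/QD against 2.06 in QD/QD, the opposite direction to RC_trough. It does not resolve the ambiguity.

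**The size is not known.** This stands. A reader might infer a fixed bias of, say, 10% to 35%. That range needs a half-life of roughly 11 to 40 h, which the documents do not supply. The remark in SAP section 8 and the PK samples at Days 21 and 42 are compatible with a longer half-life, although they do not establish one. Above about 40 h the one-compartment gap is under 10%, in arms of about 10 patients (26 × 5/13).

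**Conclusion.** The concern holds in a limited form. The interval mismatch can be read directly from Table 3, and its direction does not depend on the half-life: with identical linear pharmacokinetics, Day 14 RC_trough reads lower in BID/QD than in QD/QD. The size does depend on it: about 33% at 12 h, 17% at 24 h, 11% at 36 h, 8% at 48 h and 5% at 72 h in a one-compartment model, and somewhat less with slow absorption.

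Two stronger readings are not supported. A reader might infer that the BID/QD ratio will fall below 1 despite accumulation; in this model that needs a half-life below about 14 h. A reader might also infer that the trial's PK comparison as a whole is compromised; it is not, because the ratio is descriptive and matched quantities are planned alongside it.

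What remains is that the two values are not comparable between arms and should not be pooled in an IW-1973 overall column. Severity: minor.

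**What to change.** In SAP Table 3, calculate Day 14 RC_trough for QD/QD only, in line with the existing restriction on Day 14 RC_max. This also removes it from any pooled column. Use the Day 7 RC_trough (12 h over 12 h) as the trough accumulation ratio for BID/QD, and compare Day 14 exposure between the arms on the 24-hour C_trough. Both are already in the table.

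The cost is one line of SAP text and one derived descriptive parameter dropped in one arm. No new sample or other analysis is needed.

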8. CHANGES IN THE CONDUCT OF THE STUDY OR PLANNED ANALYSES

The following analyses will be performed in addition to those described in the study protocol.

- Change from trough baseline (defined as the Day 1 AM predose assessment) will be presented for trough supine systolic BP, diastolic BP, and pulse using the PD population.
- Change from study baseline in fasting plasma glucose, serum insulin, hemoglobin-A1C, cholesterol, HDL, LDL, triglycerides, BMI and weight that were collected as part of the safety assessments will also be analyzed using the PD population.
- Exploratory vascular physiology parameters such as Augmentation Index (AI) and AI adjusted to a heart rate of 75 beats per minute (AI-75) will also be assessed by the EndoPAT device. Change from baseline in these parameters will be analyzed using the PD population.
- Subgroup analyses of 24-hour average ABPM assessments, trough pulse and BP assessments and TEAEs by gender will be performed.
- Adverse events of clinical interest related to bleeding and hypotension will be summarized by treatment group

The following changes were made to the analyses described in the study protocol.

- Change from baseline in standing BP and pulse assessments and orthostatic changes in BP and pulse will be summarized using the Safety population instead of the PD population.
- An inadvertent typo in the unit for fasting serum insulin in the formula for HOMA-IR was revised from μ U/l to mU/l.
- Area under the plasma concentration time curve extrapolated to infinity on Day 1 will not be calculated since the 24-hour concentration-time profile does not allow for adequate characterization of IW-1973 $T_{1/2}$.

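### Day 14 Vz/F escapes the R-squared exclusion applied to t1/2, and the SAP does not say whether the Day 21 and Day 42 samples enter the shared lambda-z fit

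*SAP*

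**What the plan says.** SAP Section 7.8.1, Table 3 plans t1/2 and Vz/F on Day 14 only. Half-life comes from a log-linear regression on terminal points, with the rule "A minimum of 3 data points will be used for determination". The fit screen reads "This parameter will be calculated but not included in any summaries if goodness of fit statistic", with a cut-off of 0.800, and its subject is t1/2. The diagnostics to be reported are "Interval of the log-linear regression, number of data points, Rsq, and" lambda-z. Two rows later Vz/F is defined as "Apparent volume of distribution during the terminal phase after oral administration calculated as" CL/F over lambda-z, with no fit condition.

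SAP Section 7.8.2 then states "PK parameters will be summarized by treatment group using the PK Population". The exclusions described there concern events and procedures such as vomiting, sample processing errors and dosing errors. Poor regression fit is not among them.

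SAP Section 8 states "Area under the plasma concentration time curve extrapolated to infinity on Day 1 will not be calculated", because "the 24-hour concentration-time profile does not allow for adequate characterization of IW-1973" half-life.

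The Day 14 morning dose is the last active dose in both IW-1973 arms, since the evening dose that day is placebo (SAP Table 1). PK samples follow at 1, 3, 6, about 12 and about 24 h, then on Day 21 (±2) and Day 42 (±3) (SAP Table 2; Protocol Sections 3.8.2.10 to 3.8.3.2). Table 3 does not say which of these may enter the Day 14 terminal regression.

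**The concern.** Two gaps meet in the same lambda-z. First, the SAP treats a slope with R-squared below 0.800 as too poor to support a summarised half-life, yet lets that slope set a summarised volume. Vz/F is proportional to the fitted half-life, so a poorly determined slope carries straight through to it. Second, the set of samples eligible for the fit is left open. If the follow-up samples are left out, or are below quantification, a fit on 6, 12 and 24 h meets every written rule. That fit has the 24-hour reach which Section 8 judged too short on Day 1, so by analogy it may be too short here.

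Both parameters are listed in the Protocol (Section 3.9.3.5). With 26 patients randomised 5:5:3, each active arm has 26 × 5/13 = 10 patients, so a few unstable slopes can dominate an arm's mean or SD.

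**Working it through.** **Vz/F gap (no assumption needed).** Vz/F = (CL/F)/λz and t1/2 = ln 2/λz, so Vz/F = (CL/F) × t1/2/ln 2. CL/F is dose over AUCtau and does not use λz. Any error in t1/2 therefore passes to Vz/F in proportion. The R-squared rule removes t1/2 from the summary and leaves Vz/F in.

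**Precision of the slope.** The plan states no figure to reproduce. The documents give neither half-life nor residual error, so both are assumed: mono-exponential decline, residual SD 0.10 or 0.15 on the log scale, true half-life 20 to 60 h. For least squares, SE(λz) = σ/√Sxx, with Sxx = Σ(t − t̄)².

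- Times 6, 12, 24 h: t̄ = 14, Sxx = 64 + 4 + 100 = 168, √Sxx = 12.96.
- Times 12, 24, 168 h (Day 21 included): t̄ = 68, Sxx = 3136 + 1936 + 10000 = 15072, √Sxx = 122.8.

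At a true 40 h, λz = 0.693/40 = 0.0173 per h. With σ = 0.10 the relative SE is (0.10/12.96)/0.0173 = 45% for the short fit and (0.10/122.8)/0.0173 = 4.7% with Day 21. With σ = 0.15 the figures are 67% and 7.1%. At a true 20 h and σ = 0.10 (λz = 0.0347) the short fit has 22%. Both sets contain exactly three points, so the span makes the difference, not the count.

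**Effect of the screen.** Simulation, 200,000 profiles per case, fit on 6, 12, 24 h:

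| True t1/2 | Error | R-squared ≥ 0.80 | Median t1/2, passing | 5th–95th percentile, passing | Falling slope, fails screen |
|---|---|---|---|---|---|
| 20 h | 10% | 95.5% | 19.8 h | 14.6–30.5 h | about 4% |
| 40 h | 10% | 69% | 35.6 h | 22–79 h | 30% |
| 40 h | 15% | 51% | 30.5 h | 18–83 h | 42% |

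The pass rate depends only on half-life × error. So 20 h at 15% (product 3.0) behaves like 30 h at 10%: 82% pass, median 28.4 × 20/30 = 18.9 h. Likewise 60 h at 10% matches 40 h at 15%: 51% pass, median 45.8 h.

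**What reaches Vz/F.** At a true 40 h, the fits that fail the screen have half-lives with 5th–95th percentiles of about 29–259 h (10% error) or 24–396 h (15%). With CL/F correct, Vz/F at the upper end is 259/40 = 6.5 or 396/40 = 9.9 times its true value. In an arm of 10, a 30–42% failure rate is 3 to 4 patients.

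**With Day 21 quantifiable.** Fitting 12, 24 and 168 h at a true 40 h, essentially all fits pass, with 5th–95th percentiles of 37–43 h (10%) or 36–45 h (15%).

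**Will Day 21 be quantifiable?** The fraction remaining at 168 h is 2^(−168/t1/2): 2^(−8.4) = 0.3% at 20 h and 2^(−4.2) = 5.4% at 40 h. The quantification limit is not given. The sample is most likely to be available where the short fit is weakest.

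**The case against.** A reader might infer that Section 8 itself calls the Day 14 profile inadequate for half-life. It does not. That sentence concerns AUCinf on Day 1, where later dosing cuts the profile off, and Table 3 is consistent with it in planning t1/2 and Vz/F on Day 14 only. Nor is Day 14 just a 24-hour profile: no active dose follows, samples are scheduled about 7 and 28 days later, nothing in the SAP excludes them, and actual sampling times are used. An analyst could include them under the existing text. What stands is that the SAP does not say so.

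A reader might also infer that the summarised half-life will be biased low and very imprecise. That depends on assumptions the documents cannot confirm. At 20 h and 10% error the loss is slight. Nor should the case rest on how often pure noise passes a three-point screen, since that calculation assumes no decline and counts rising slopes, which give no half-life.

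There are partial safeguards. The regression interval, number of points and R-squared are reported. The effective half-life from RAUCtau does not use lambda-z. SAP Section 5.4 makes PK calculation conditional on adequate data, and any inferential statistics are for description only. These limit the consequences, but none removes a rejected lambda-z from the Vz/F summary.

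**Conclusion.** The concern holds as a minor wording gap in two parts. That Vz/F lacks the exclusion applied to t1/2 follows from the text alone. That the Day 14 regression may be confined to 6, 12 and 24 h is permitted by the text, not required by it, and Section 8 bears on it only by analogy. The size is conditional on assumed mono-exponential decline, half-life and residual error: small at 20 h and 10% error, and large at 40 h and 10–15% error, where 3 to 4 of 10 patients per active arm could feed Vz/F from a slope judged unfit for t1/2. No decision in the trial rests on either parameter.

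**What to change.** Change Table 3 (Day 14) in two places.

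1. In the Vz/F row, apply the same R-squared < 0.800 exclusion from summaries as for t1/2.
2. In the t1/2 row, state that the Day 21 sample, and the Day 42 sample if quantifiable, enters the Day 14 lambda-z regression whenever it is quantifiable and lies on the terminal phase.

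The second change matters more. The exclusion alone makes the two parameters consistent but does not cure a short fit: passing fits at a true 40 h have a median of 30.5–35.6 h, so Vz/F would be summarised at about 0.76–0.89 of its true value.

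A rule that the fitted interval must span two estimated half-lives would not be a good fallback when Day 21 is below quantification. Over 6 to 24 h it requires an estimate of 18/2 = 9 h or less, so for a true half-life of 20 h or more it would keep only falsely steep slopes.

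The cost is SAP wording, since the samples are already scheduled. The downside is that fewer patients contribute to the Vz/F summary. A late sample also has high leverage, hence the terminal-phase condition.

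### The effective half-life formula in SAP Table 3 fits only once-daily dosing but applies to every patient, so identical linear PK would read roughly 20–50% longer in BID/QD

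*SAP*

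**What the plan says.** SAP 7.8.1 states that the Table 3 parameters "will be calculated for each patient, whenever possible, if systemic levels of IW-1973 are quantifiable". In the Day 14 part of that table:

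- **Effective half-life.** "Effective half-life, calculated as" ln(2) × (−24) / ln(1 − 1/RAUCtau). The interval is fixed at 24 h and no regimen is named.
- **RAUCtau.** An accumulation ratio "comparing Day 14 with Day 1, calculated as" Day 14 AUCtau over Day 1 AUCtau for QD/QD. The other active arm is printed as "QD/BID regimen: Day 14" AUCtau over Day 1 AUC24. No such arm exists, so BID/QD must be meant.
- **RCmax.** A ratio "comparing Day 14 with Day 1 calculated for the QD/QD regimen only".

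The Day 1 AUCtau row defines AUC24 for patients dosed twice daily: "this parameter will be calculated for the morning and for the evening dose, and for the 24-hour sampling period on Day 1". SAP Table 1 (3.2) gives BID/QD patients 20 mg in the morning and 20 mg in the evening on Days 1 to 7, then 40 mg each morning.

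SAP 7.8.2 adds: "PK parameters will be summarized by treatment group using the PK Population". SAP 6.1 also calls for an overall IW-1973 summary of PK parameters unless otherwise indicated.

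**The concern.** The formula inverts R = 1/(1 − exp(−24k)), the accumulation ratio when one fixed dose is given every 24 h. QD/QD meets that condition. The BID/QD ratio compares a 40 mg once-daily interval on Day 14 with a first day of two half-doses, the second observed for only 12 h. Its denominator is smaller for reasons of timing alone, and the formula turns that shortfall into extra half-life.

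The study objective is to compare, among other things, the PK profile of the two regimens. A by-arm table would show a longer effective half-life in BID/QD with nothing to tell the reader that it is an artefact, and an overall column would mix the two scales.

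**Working it through.** The plan states no half-life, RAUCtau value or absorption rate, so there is no figure of its own to reproduce. The check is of the formula.

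**Inputs from the SAP.** The regimens (Table 1), the RAUCtau definitions and the half-life formula (Table 3).

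**Assumed.** Linear PK, identical in both arms; the half-lives and absorption rate constants (ka, per h) shown below.

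**Direction.** Let F(t) be the single-dose AUC from 0 to t, per mg.

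- Day 1, QD/QD: 40·F(24).
- Day 1, BID/QD: 20·F(24) + 20·F(12).
- Day 14: the same AUCtau in both arms at steady state.

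So RAUCtau(BID/QD) / RAUCtau(QD/QD) = 2/(1 + p), with p = F(12)/F(24). Since p < 1, this always exceeds 1, whatever the shape of the linear profile. The formula increases with RAUCtau, so the half-life is inflated as well.

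**One case by hand.** One compartment, bolus input, true half-life 24 h, steady state:

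- F(24) is proportional to 1 − 0.5 = 0.5 and F(12) to 1 − 0.7071 = 0.2929, so p = 0.586.
- The ratio of RAUCtau is 2/1.586 = 1.261. RAUCtau is 2.000 in QD/QD and 2.522 in BID/QD.
- QD/QD: 16.636 / −ln(1 − 1/2.000) = 16.636/0.693 = 24.0 h, the true value.
- BID/QD: 16.636 / −ln(1 − 1/2.522) = 16.636/0.505 = 32.9 h.

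**Exact 14-day superposition, including the Day 8 switch, one compartment.** Effective half-life in hours, QD/QD vs BID/QD (ratio):

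| True half-life | Bolus | ka 1 | ka 0.5 | ka 0.3 |
|---|---|---|---|---|
| 12 h | 12.0 vs 17.0 (1.41) | 12.5 vs 18.1 (1.44) | 13.2 vs 19.4 (1.47) | 14.2 vs 21.5 (1.52) |
| 24 h | 24.0 vs 33.0 (1.38) | 25.1 vs 35.0 (1.40) | 26.3 vs 37.4 (1.43) | 28.1 vs 41.1 (1.46) |
| 48 h | 47.6 vs 64.9 (1.36) | 49.6 vs 68.8 (1.39) | 51.9 vs 73.3 (1.41) | 55.4 vs 80.1 (1.45) |
| 72 h | 68.8 vs 93.8 (1.36) | 71.8 vs 99.4 (1.38) | 75.1 vs 105.7 (1.41) | 80.0 vs 115.3 (1.44) |

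**Two compartments.** 256 cases: initial half-life 2–6 h, terminal 24–72 h, fast coefficient fraction 0.3–0.85, the same four inputs. Excess in BID/QD:

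- bolus 19–35%, ka 1 21–37%, ka 0.5 23–40%, ka 0.3 26–44%;
- smallest: initial 3 h, terminal 72 h, fraction 0.85, bolus; RAUCtau 2.71 vs 3.13, half-life 36.1 vs 43.1 h (1.19);
- largest: initial 6 h, terminal 24 h, fraction 0.3, ka 0.3; half-life 24.7 vs 35.5 h (1.44).

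Over all cases RAUCtau is 12–40% higher in BID/QD. AUCs computed by the linear-up/log-down rule at the scheduled sampling times, rather than exactly, move the half-life ratio by less than 0.03.

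**The case against.** **It is one descriptive parameter.** Effective half-life is absent from the PK list in Protocol 3.9.3.5 and from the plotted parameters in SAP 7.8.3. No test, decision rule or stopping criterion uses it, and Day 14 AUCtau, Cmax, Ctrough, CL/F and terminal half-life are unaffected. This stands and limits the severity. It does not make the by-arm values right.

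**The denominators are printed separately, and wording such as whenever possible leaves discretion.** The RAUCtau row does show the difference. But because it supplies a ratio for BID/QD, the half-life can be computed there, and nothing tells the analyst not to. The authors did write such a limit for RCmax.

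**The range depends on the models chosen.** It does. A 6 h half-life or slower absorption takes the excess to about 49–66%. A fast coefficient fraction of 0.95–0.98 takes it down to about 8–23%. So 19–52% describes the cases run and is not a bound. SAP section 8 drops Day 1 AUCinf "since the 24-hour concentration-time profile does not allow for adequate characterization of IW-1973" half-life, which may argue against a half-life as short as 12 h, but sparse sampling could equally explain it.

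**The formula is inexact in QD/QD too.** With ka 0.3 a true 12 h reads 14.2 h, and with bolus input a true 72 h reads 68.8 h because Day 14 is short of steady state. QD/QD is nonetheless the setting the formula is derived for; in BID/QD a further, systematic upward error is added.

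**BID/QD could be given its own inversion.** Under one compartment and rapid input, x = [−1 + √(1 + 8(1 − 1/RAUCtau))]/2 and half-life = 12·ln(2)/(−ln x). RAUCtau 2.522 then returns 24.0 h. The gap to QD/QD shrinks to 0–9% in the one-compartment cases above and to between −14% and +5% in the two-compartment cases. This is a workable alternative, but it rests on that model.

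**Conclusion.** The concern holds. As written, the plan calculates effective half-life in BID/QD from a ratio that does not satisfy the formula's premise. Given linear and identical PK, the BID/QD value is biased upward relative to QD/QD; that direction needs no compartment model. The size does: 19–52% over the cases run, with values outside that range possible under other absorption or distribution assumptions. Differences between morning and evening doses from food or time of day were not modelled. The error should be corrected because it creates an apparent difference between the regimens under comparison, but its reach is one descriptive parameter and any overall column that includes it.

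**What to change.** Make two wording changes in the Day 14 part of SAP Table 3:

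1. In the effective half-life row, state that it is calculated for QD/QD patients only, mirroring the RCmax row.
2. In the RAUCtau row, correct the arm label to BID/QD and add that this ratio is descriptive, at equal total daily dose, and not comparable with QD/QD accumulation.

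No new data or sampling are needed. The cost is that effective half-life is reported for about 10 patients instead of 20 (26 patients at 5:5:3 gives 10, 10 and 6). If values in both active arms are wanted, the BID-specific inversion can be prespecified with its model assumption stated.
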